5.1.4 Considerations for base MMRM model for change from baseline analyses

The observed value and change from baseline for a parameter of interest will be summarized by treatment group at each post-baseline visit. A mixed model repeated measures (MMRM) model will be used as the primary analysis to analyze change from baseline using fixed effects of treatment group, time (categorical), treatment group-by-time interaction, baseline for the parameter of interest, (baseline for the parameter of interest) by time interaction, baseline Color Trails 2 test (≤ 170 or > 170 seconds) and region (see healthcare region definitions in Section 3.1). An unstructured covariance matrix will be used to model the within-subject variance-covariance errors. If the unstructured covariance structure matrix results in a lack of convergence, the heterogeneous Toeplitz covariance structure followed by the heterogeneous first-order autoregressive covariance structure will be used. The Kenward-Roger approximation will be used to estimate the denominator degrees of freedom. If the unstructured variance-covariance structure does not converge in the MMRM model and a structured model is used, the sandwich estimator will be used to get the variance of the treatment effect estimator. The adjusted mean of each treatment group, as well as the treatment group differences will be displayed with 95% CI and p-value. In the primary analysis of each endpoint, missing data are assumed to be missing at random [Rubin 1976].

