7.2. Method of Treatment Assignment

All participants will be centrally randomized using an Interactive Response Technology (IRT). Before the study is initiated, each user will receive log in information and directions on how to access the IRT. Randomization will be stratified by country and screening CTT Part 2 stratum of a score either less than or equal to 170 seconds or greater than 170 seconds. Randomization will only be stratified by screening CTT Part 2 stratum under the IRT system for protocol Version 1. To promote treatment balance within each country, randomization will be stratified by both country and screening CTT Part 2 when the new IRT system for this protocol is in place.

Study treatment will be dispensed at the study visits as listed in Schedule of Activities (Section 2).

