17.4.1. Efficacy Analyses

Efficacy analyses will be performed using the intent-to-treat participants. Unless stated otherwise, all tests of treatment effects will be conducted at a two-sided significance level of 0.05. The primary efficacy analyses will be for comparative efficacy of BIIB092 to placebo in the double-blind treatment period (including all data through Week 52 for participants discontinuing study treatment during the double-blind period). Details of the efficacy analyses for the open-label extension period will be provided in the statistical analysis plan.

Endpoint	Statistical Analysis Methods
Primary	Changes from baseline in PSPRS will be analyzed using a restricted maximum likelihood (REML)-based Mixed Model with Repeated Measures (MMRM) approach. The principal analysis of the primary endpoint will be a MMRM model that will include treatment, visit, treatment-by-visit interaction, stratification factors as categorical fixed effects, baseline value of PSPRS as a continuous covariate, and baseline value of PSPRS-by-visit interaction. An unstructured covariance matrix will be used to model the within-participant errors. If this analysis fails to converge, the following structures will be tested in this order: the heterogeneous Toeplitz covariance structure, autoregressive model of order 1, and compound symmetric. The first covariance structure yielding convergence will be used.

CONFIDENTIAL

The information contained herein may not be used, disclosed, or published without the written consent of Biogen MA Inc.

Endpoint	Statistical Analysis Methods

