1.2 Number of Participants

It is anticipated that approximately 459 male and female participants will be dosed in this study. Approximately 459 participants will be randomly assigned, in 2:1 ratio, to receive 2000 mg of BIIB092 or placebo (306 participants active and 153 placebo) administered by IV approximately once Q4W. Randomization is stratified by country and screening Color Trails Test (CTT) Part 2 completion time of either ≤ 170 or > 170 seconds. Anticipating a dropout rate of approximately 25%, approximately 345 participants (230 participants in the BIIB092 treatment group and 115 participants in the placebo group) are expected to complete the study through Week 52.

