3 GENERAL CONSIDERATIONS

3.1 General Methods

This statistical analysis plan (SAP) only covers the analyses for the double-blind placebo-controlled portion of the study. Hereafter, the double-blind, placebo-controlled portion of the study will be referred to as “the study” in the rest of this SAP (e.g., completion of the study means completion of the placebo-controlled portion). A separate SAP will be prepared for the analyses of the open label extension (OLE) period and integrated analyses across both portions of the study. The analyses of selected exploratory endpoints may be documented separately. The term “subject” used in this SAP and in the analyses is equivalent to the term “participant” used in the Protocol.

Summary tables will be presented using descriptive summary statistics. For continuous variables, summary statistics will generally include: number of subjects with data, mean, standard deviation, median, 25% percentile, 75% percentile, minimum and maximum. For categorical variables, this

will generally include: number of subjects randomized or dosed, number with data, and the percent of those with data in each category.

In general, listings will include all data in the placebo-controlled and OLE periods (all data in the study), with an indicator of the study period (screening, placebo-controlled, or OLE) for each record to indicate when the event occurred.

Unless otherwise specified, baseline value is defined as the most recent non-missing measurement collected prior to the first dose. Change from baseline will be defined as post-baseline value minus baseline value.

Unless stated otherwise, all statistical tests will be 2-sided with statistical significance level of 0.05.

The statistical software SAS® will be used for all summaries and analyses.

The health care region used in the analysis (referred as region in this SAP) is defined as:

- US: United States
- Non-US: Australia, Austria, Canada, France, Germany, Greece, Italy, Russian, Spain, United Kingdom, Japan and Korea

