4.1 Accounting of subjects

Disposition will be summarized for the randomized subjects population by treatment group and the summary data will include number (%) of subjects randomized and dosed, number (%) of subjects who completed the treatment/study, and number (%) of subjects who discontinued treatment and/or withdrew from study. The number of subjects discontinued from study treatment/withdrew from study will also be summarized by treatment group and by baseline 28-item and 15-item PSPRS total score (\leq median, $>$ median). For subjects who discontinued treatment and/or withdrew from study, the reasons for discontinuation and/or withdrawal, and days on treatment and days on study will be summarized and listed. The number of subjects discontinuing treatment will be summarized in time intervals, i.e., 0 to $<$ 12 weeks, \geq 12 to $<$ 24 weeks, \geq 24 to $<$ 36 weeks, \geq 36 to $<$ 48 weeks, and \geq 48 weeks. A similar summary will be done for subjects who withdrew from study. Number of subjects excluded from the per-protocol population will also be summarized. Time to treatment discontinuation and time to study withdrawal will be displayed by Kaplan-Meier plot by treatment group.

The number of subjects in each analysis population will be summarized. The number of subjects dosed will be summarized by region as defined in Section 3.1, country and site. In addition, the number of subjects who completed the treatment/study will be summarized by region, country and site.

A randomization listing including country, CTT 2, randomization number, randomization date, and the protocol version, as well as a listing of randomized subjects excluded from the ITT

population, and a listing of dosed subjects excluded from the PP population will be provided. Subjects with a mismatch between randomization CTT 2 categorization and actual CTT 2 categorization will be listed.

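### The SAP's primary MMRM adjusts for region and baseline CTT2 instead of the randomisation strata (country and screening CTT2), and no planned analysis uses the strata as randomised

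*SAP*

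**What the plan says.** **Protocol.** Section 17.4.1 specifies the primary MMRM with "stratification factors as categorical fixed effects", and asks for the same factors in the Week 52 ANCOVA. Section 7.2 names them: "Randomization will be stratified by country and screening CTT Part 2 stratum", cut at 170 seconds. It then qualifies this for early participants: "Randomization will only be stratified by screening CTT Part 2 stratum under the IRT system for protocol Version 1". Country joined the scheme only with the newer IRT system.

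**Placebo-controlled SAP.** Section 1.2 repeats the scheme: "Randomization is stratified by country and screening Color Trails Test (CTT) Part 2 completion time". The base MMRM in 5.1.4 has treatment, visit, their interaction, the baseline score, its interaction with visit, a baseline CTT2 category split at 170 seconds, "and region (see healthcare region definitions in Section 3.1". Section 3.1 sets the US against a single second level: "Non-US: Australia, Austria, Canada, France, Germany, Greece, Italy, Russian, Spain, United Kingdom, Japan and Korea". The 5.2.4.3 ANCOVA, the CGI-C model (5.3.1.2), the pattern-mixture imputation model (5.2.4.5) and the slope model (5.2.5.6) write out the same two terms.

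Section 4.1 provides two relevant listings: "A randomization listing including country, CTT 2, randomization number, randomization date, and the protocol version"; and "Subjects with a mismatch between randomization CTT 2 categorization and actual CTT 2 categorization will be listed".

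**The concern.** The two documents specify different primary models. The protocol's model contains the factors that governed randomisation. The SAP's model collapses one of them to two levels and takes the other at a different time point. The change carries through to the key secondary models, and none of the sensitivity or supplementary analyses in SAP Table 1 returns to the randomised strata.

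When randomisation balances the arms within strata, the treatment estimate benefits from that balance whether or not the strata are modelled. The model-based standard error reflects the benefit only if they are. Leaving out a stratum that predicts progression therefore tends to overstate the standard error. At stake are a little precision and a clear answer to which model is the prespecified one.

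**Working it through.** **Is baseline CTT2 the randomised stratum?** Protocol Table 1 schedules the CTT at screening, and Table 2 schedules it again at Week 0. SAP 3.1 defines baseline as the latest value before first dose; the baseline row of SAP Table 4, which covers the CTT, says on or before the first-dose date. So the Week 0 value normally supersedes the screening value. SAP 5.1.2 also sets a CTT score missing through refusal or impairment to 240 seconds. A participant at or below 170 seconds at screening who refuses at Week 0 could thus move to the upper category. The SAP does not say whether that imputation comes before the rule taking the latest non-missing value.

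**Is region the country stratum?** The non-US list holds 12 countries, so 13 countries become 2 levels. Country by CTT2 gives 13 × 2 = 26 cells, on average 459/26 = 17.7 randomised and 345/26 = 13.3 completers per cell.

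**The plan's own power figure.** Inputs from protocol 17.1: 230 + 115 completers, difference 3.2, SD 9.95, two-sided 0.05.

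SE = 9.95 × √(1/115 + 1/230) = 1.136; 3.2/1.136 = 2.816; power = Φ(2.816 − 1.960) = 80.4% (80.2% with the noncentral t on 343 df). The stated 80% reproduces. It is an unadjusted t-test, so the covariates do not enter it.

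**Size of the mismatch in the MMRM.** The documents give no variance shares for country or CTT2, so these are assumed. I simulated 5,000 trials in each of 16 scenarios.

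- From the documents: N = 459, 2:1, five post-baseline visits, 25% dropout, Week 52 SD 9.95, effect −3.2, unstructured covariance, the 5.1.4 terms.
- Assumed: blocks of 3; US share 35%, smallest country 1%; random monotone dropout; random slopes; visit error SD 3.5; baseline PSPRS share 3%; CTT2 test-retest correlation 0.8, so that 20% change category; covariate effects growing with time unless stated.

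The comparison model has country, the screening CTT2 stratum and baseline CTT2. The SE column is (SAP SE / comparison SE − 1); the power change is comparison minus SAP.

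| Predictor (assumed share of variance) | SE, SAP / comparison | SAP SE excess | Power, SAP / comparison (%) | Change (points) |
|---|---|---|---|---|
| Neither | 1.0613 / 1.0617 | −0.04% | 85.4 / 85.3 | −0.1 |
| Country 10% | 1.0489 / 1.0395 | +0.9% | 86.9 / 87.4 | +0.5 |
| Screening CTT2 5% | 1.0593 / 1.0540 | +0.5% | 86.2 / 86.5 | +0.3 |
| Baseline CTT2 5% | 1.0531 / 1.0536 | −0.05% | 85.6 / 85.5 | −0.1 |
| Country 10% + screening CTT2 5% | 1.0458 / 1.0289 | +1.6% | 86.4 / 87.4 | +1.0 |
| Same, effects constant from Week 12 | 1.0286 / 0.9841 | +4.5% | 87.5 / 89.3 | +1.8 |

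Other results:

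- Country 10% with 25% or 50% of participants randomised under the Version 1 IRT (assumed proportions): +0.4 and +0.5 points.
- Both CTT2 categories measuring one trait (5%): +0.1% in SE, −0.1 points.
- Baseline CTT2 the true predictor and replaced by the screening stratum: SE rises from 1.0531 to 1.0589, about half a percent, and 0.7 points of power are lost.
- SAP type I error: 3.8% to 5.3% over all 16 scenarios (Monte Carlo SE 0.3 points). The paired Monte Carlo SE of the power changes is 0.1 to 0.2 points.

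**A cruder cross-check.** A Week 52-only linear model (n = 345, 3,000 runs per scenario, no baseline PSPRS or earlier visits, CTT2 share up to 10%, up to 30% changing category) compared the SAP terms with country and the screening stratum. SAP type I error was 3.1% to 5.1%, its SE about 0 to 9% larger and its power 0 to about 5 points lower. The direction is the same. The upper end is higher because the assumed shares and category changes are larger and no other covariates or visits are used.

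**The case against.** The case for leaving the SAP alone is substantial.

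- **Little follows from it.** Every SAP power figure in the table is above 85%, against a planned 80%, and the largest gain needs three favourable assumptions together. This stands and sets the severity.
- **The protocol defers to the SAP.** Section 17.4 calls its text a summary and leaves detail to a SAP finalised before database lock, and region is prespecified there. That makes the change legitimate, but it neither explains it nor shows whether the result depends on it. SAP 5.2.4.1, by contrast, does reconcile its imputation method with the protocol's name for it.
- **Country was not a stratum for everyone, and pooling sparse countries is sensible.** Both stand. A reader might infer that country must replace region in the primary model; with the Version 1 IRT participants stratified on CTT2 only, the documents do not require that.
- **Screening falls within 42 days of first dose and uses the same test.** If both categories measure one trait, the screening stratum adds nothing. This stands, and is why the stratum should be added and not substituted.
- **SAP 4.1 may mean something else.** A reader might take its mismatch listing as an admission that screening and baseline categories differ. The SAP does not define the actual category; it could mean the true screening value against a wrong IRT entry. The listing may therefore miss screening-to-baseline changes altogether.
- **A reason may be written down.** The SAP's contents list a section on changes from Version 1 that cannot be read here, so it cannot be said that no justification exists.

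**Conclusion.** The departure from protocol 17.4.1 is clear on the text: region for country, a normally Week 0 CTT2 category for the screening stratum, and no planned analysis with the strata as randomised. The severity is minor. Inference is neutral to slightly conservative, and including the strata changes power by about −0.1 to +1.8 points in the MMRM simulation. That range rests on assumed variance shares, country sizes and CTT2 repeatability, and on a comparison model that changes country and CTT2 together; for the CTT2 stratum alone, the +0.3 row is the nearer guide.

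A reader might infer that departing from the strata inflates type I error or undermines the primary test. Nothing supports that: the simulated error rates stayed at or below nominal within simulation error.

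**What to change.** 1. In SAP 5.1.4, add the screening CTT2 stratum as recorded in IRT and keep baseline CTT2 as a further term. Region may stay.
2. Carry both CTT2 terms into the key secondary MMRMs (including CGI-C), the 5.2.4.3 ANCOVA, the 5.2.5.6 slope model and the 5.2.4.5 imputation model, so that imputation and analysis models agree. In 5.3.2.5, state that both CTT2 terms are dropped when CTT2 is the endpoint.
3. In 5.2.4, add one prespecified sensitivity analysis with country in place of region and the IRT CTT2 stratum. Fix the pooling rule before unblinding, for example one group for non-US countries with fewer than 10 analysed participants.
4. In 4.1, define the actual CTT2 category. State the reason for using region, if it is not already given.

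The cost is wording, model statements and a pooling rule. The randomisation listing in 4.1 already holds country, CTT2 and protocol version. Adding the stratum uses 1 degree of freedom and costs about 0.01% in SE. Country uses at most 11 more (12 − 1) out of about 340. If neither factor predicts, country plus both CTT2 terms costs under 0.1% in SE in an MMRM and about 0.4% in a Week 52-only model.

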5.2 Primary Efficacy Endpoint

Two primary endpoints meeting evidentiary requirements of the US, and Europe/Japan, respectively were selected: change from baseline in 15-item PSPRS at Week 52 (US); and change from baseline in 28-item PSPRS at Week 52 (Europe and Japan). For each region, only the endpoint which met evidentiary requirements of the region is considered primary and the other is considered a non-key secondary endpoint.

The original PSPRS comprises 28 items in 6 areas. Six items (1, 2, 20-23) are rated on a 3-point scale (0-2) and 22 remaining items are rated on 5-point scale (0-4). Six subscale scores are auto-calculated as follows:

- History: sum of 7 item scores with total maximum score of 24 points: item 1 withdrawal, item 2 irritability, item 3 dysphagia for solids, item 4 knife and fork, item 5 falls, item 6 urinary incontinence, item 7 sleep difficulty;
- Mentation: sum of 4 item scores with total maximum score of 16 points: item 8 disorientation, item 9 bradyphrenia, item 10 emotional incontinence, item 11 grasping;
- Bulbar: sum of 2 item scores with total maximum score of 8 points: item 12 dysarthria and item 13 dysphagia for liquids;
- Ocular: sum of 4 item scores with total maximum score of 16 points: item 14 upward eye movement, item 15 downward eye movement, item 16 left-right eye movement, item 17 eyelid dysfunction;
- Limb: sum of 6 item scores with total maximum score of 16 points: item 18 limb rigidity, item 19 limb dystonia, item 20 finger tapping, item 21 toe tapping, item 22 apraxia of hand movement, item 23 tremor;
- Gait: sum of 5 item scores with total maximum score of 20 points: item 24 neck rigidity, item 25 arising from chair, item 26 gait, item 27 postural stability, item 28 sitting down.

5.2.1 Primary endpoint for United States (US)

Fifteen items were selected from the original 28-item PSPRS to form a 15-item PSPRS: items 3, 4, 5, 12, 13, 14, 15, 16, 17, 19, 24, 25, 26, 27, and 28. Among these 15 items, response options of 13 items will be collapsed and rescored (details are provided in Section 11.1)

Based on factor analysis of pooled historical data, three domains were identified: gait/limb function (8 items, including items 4, 5, 19, 24-28), ocular motor (4 items, including average of items 14-16 and item 17), and bulbar (3 items, including items 3, 12, 13). The change from baseline at Week 52 in this 15-item PSPRS total score is used as the primary endpoint for US. The terms “15-item PSPRS” and “15-item PSPRS total score” will be used interchangeably. The 28-item PSPRS will be included in the dossier as supportive information for the US.

5.2.2 Primary endpoint for Europe and Japan

The original 28-PSPRS total score is auto-calculated as the sum of all 28 item scores, and ranges from 0 (normal) to 100 points. The change from baseline at Week 52 in this 28-item PSPRS is the primary endpoint for Europe and Japan. The terms “28-item PSPRS” and “28-item PSPRS total score” will be used interchangeably. The 15-item PSPRS will be included in the dossier as supportive information for Europe and Japan.

5.2.3 Primary analysis

The primary analysis of the primary endpoints, change from baseline in 15-item and 28-item PSPRS at Week 52, is the treatment policy approach [ICH E9 (R1) Addendum 2014, 2017]. The estimand of the primary analysis is defined as:

- Population: all subjects in the ITT population
- Variable: change from baseline in PSPRS at Week 52
- Handling of intercurrent events: regardless of intercurrent events (example, treatment discontinuation)
- Summary statistics: difference in variable means between treatment groups

The primary analysis will be based on the MMRM model described in Section 5.1. A line plot of adjusted mean change from baseline over time and a bar plot of results at Week 52 will also be provided.

In addition to this primary analysis, some sensitivity analyses (Section 5.2.4) and supplementary analyses (Section 5.2.5) will be performed. Forest plots of adjusted mean change from baseline versus placebo at Week 52 from primary, sensitivity and supplementary analyses will be provided. A listing of primary endpoints will be provided.

5.2.4 Sensitivity analysis

The following sensitivity analyses will be performed to assess the robustness of the primary analysis to deviation from the missing-at-random assumption. All the sensitivity analyses will be conducted for the ITT population for both 15-item and 28-item PSPRS.

5.2.4.1 Copy increment from reference (CIR) method

The CIR method (which is the same as the copy difference from control method described in the study protocol) will be applied to impute the post-withdrawal data for any subject assigned to BIIB092 treatment who withdraws from study early based on data from the placebo group rather than the subject's own randomized treatment group [Carpenter et al. 2013]. Specifically, for a subject assigned to BIIB092 treatment who withdraws early, his or her mean trajectory after early withdrawal is assumed to be parallel to the mean trajectory of the placebo group, and the difference between the two means is the same as the difference at the time of withdrawal. This method assumes that any benefit gained from previous treatment will be retained, but subjects progress as if they were on placebo after withdrawal from study. For any subject on placebo who withdraws early, his or her post-withdrawal profile will be imputed following the missing-at-random principle. Implementation details can be found in Section 11.2.1.

After all missing data have been imputed, MMRM model described in Section 5.1 will be applied for analysis.

